2.2 Background/prevalence of research topic

Endometriosis is an estrogen dependent disease present in 25-35% of infertile women. Given controlled ovarian hyperstimulation leads to development of multiple follicles and considerable rise in serum estradiol concentrations, patients and providers must consider the possible risk of disease and symptom progression related to controlled ovarian hyperstimulation. This may be especially true with repeated stimulations.

With respect to disease progression, data have been contradictory, but overall favor that there is no significant risk of disease progression with controlled ovarian hyperstimulation. The impact of controlled ovarian hyperstimulation on endometriosis related symptoms is less clear, with a single prospective cohort study of 64 patients with endometriosis, published in 2011, showing no marked worsening in symptoms [7]. Study limitations include lack of a control group, small sample size and a limited follow-up time of 3-6 months. Anecdotally, providers from our institution's Center for Reproductive Health and Center for Endometriosis do feel patients often report a flare in endometriosis related symptoms following controlled ovarian hyperstimulation. Overall, the question remains open and further investigation is warranted.

Additionally, the impact of endometriosis on in vitro fertilization outcomes has been a long-debated topic, with some studies showing poorer outcomes compared to controls and others showing no impact. Prolonged use of a GnRH agonist before in vitro fertilization with embryo transfer, in patients with endometriosis, has been associated with significantly higher ongoing pregnancy rates [8, 9].

3 - Rationale/Significance

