4.2 Primary Objective

To evaluate the impact of ovarian hyperstimulation on endometriosis-related symptoms.

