5.2.1 Primary Outcome Variables

- To compare the mean endometriosis pain score at baseline, 6 and 12 weeks following egg retrieval.
- To evaluate how endometriosis pain scores change throughout controlled ovarian hyperstimulation.

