5.2.2 Secondary and Exploratory Outcome Variables (if applicable)

- To compare the mean endometriosis pain score at baseline, 6 and 12 weeks following egg retrieval in the placebo, letrozole and control groups.
- To compare how endometriosis pain scores change throughout controlled ovarian hyperstimulation in the placebo, letrozole and control groups.
- To compare egg/embryo quantity and quality in the placebo, letrozole and control groups. This will include evaluation of: total oocyte yield per starting antral follicle count, total mature oocyte yield per oocytes collected, embryo yield per starting antral follicle count, embryo yield per oocyte retrieved, fertilization rate per mature oocyte retrieved, ovarian follicular fluid hormone levels.
- To compare pregnancy rates per embryo transfer in the placebo, letrozole and control groups.

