5.3.1 Number of Participants

We will be aiming for a total of 40 participants with a prior diagnosis of endometriosis. Of those 40 participants, 20 participants will be randomized to the placebo group and 20 participants will be randomized to the letrozole group. We will also enroll 20 age-matched controls without a history of endometriosis. This will result in 60 study participants.

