6.3 Study Procedures

Management of participants' ovarian stimulation will be done by their primary doctor based on their knowledge, expertise and established standard of care guidelines. Participants will come to the clinic for transvaginal ultrasound visits to track follicle development, and blood draws will be completed per routine. Serum estradiol levels will be run on all participant blood samples at the end of the study to assure blinding of patients and providers, as discussed in section 6.1.3 above. When follicles are an adequate size, participants will be instructed to take a trigger shot, an injectable hormone medicine that helps to prepare eggs for retrieval. On the day of the egg retrieval procedure, the treating physician will use standard of care transvaginal aspiration to drain all of the visible follicles in order to retrieve eggs. After the egg has been isolated, the excess fluid and cells are usually discarded. We will collect the follicular fluid from the first follicle aspirated in each ovary to perform hormone assays. Throughout the ovarian stimulation process, participants will be asked to complete electronic surveys about symptoms they are experiencing related to their endometriosis.

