6.4.1 Statistical Design

An intention-to-treat analysis of the results will be used, meaning results of the study will be based on the initial treatment assignment and not the treatment eventually received. The primary outcome will be assessed by changes in pain survey scores before, during and following controlled ovarian hyperstimulation.

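### The primary objective is assessed by pain-score change over time with no comparator, and the only stated tests are two-sample and sized for letrozole against placebo, so no stated analysis separates an endometriosis-specific change from discomfort common to stimulated women

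*Combined protocol and SAP*

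**What the plan says.** **Objective and outcomes.** Section 4.2 sets the primary objective: "To evaluate the impact of ovarian hyperstimulation on endometriosis-related symptoms". Section 5.2.1 gives two primary outcomes, "To compare the mean endometriosis pain score at baseline, 6 and 12 weeks following egg retrieval" and "To evaluate how endometriosis pain scores change throughout controlled ovarian hyperstimulation". Neither names a group or a comparator. Section 6.4.1 agrees: "The primary outcome will be assessed by changes in pain survey scores before, during and following controlled ovarian hyperstimulation".

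**Controls.** Section 5.3.1 states: "We will also enroll 20 age-matched controls without a history of endometriosis". Section 6.1.2 gives them the usual gonadotropins and trigger. The Synopsis design paragraph, which covers all 60 participants, sets one survey schedule: baseline, trigger day, and 3, 6 and 12 weeks after retrieval. The comparison with controls is a secondary outcome in 5.2.2 ("To compare how endometriosis pain scores change throughout controlled ovarian hyperstimulation in the placebo, letrozole and control groups") and again in 6.4.3.2. Neither section specifies a contrast or a test for the three groups.

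**Tests.** Section 6.4.2 names the primary outcome as a pre-to-post change in pain score. It then specifies a two-sample test under 1:1 randomisation, with 20 per group. Section 6.4.3.1 gives a two-sample t-test or rank-sum test for pain scores. No paired or one-sample test appears anywhere.

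**Background.** Of the one earlier cohort, section 2.2 says: "Study limitations include lack of a control group, small sample size and a limited follow-up time of 3-6 months".

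**The concern.** The objective, the outcome and the test do not point at the same comparison. The outcome is a before-after change, and the test compares two randomised arms. Both arms consist of stimulated women with endometriosis, so the difference between them estimates the effect of letrozole, which is the secondary objective in 4.3.

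That leaves the before-after change to carry the primary conclusion. Survey 2 falls on trigger day, at the end of stimulation, and survey 3 comes three weeks after transvaginal aspiration. A woman without endometriosis may also have pelvic discomfort at those times. A rise in the endometriosis arms cannot by itself be called a worsening of endometriosis symptoms. Section 2.2 regards the lack of a control group as a limitation, and this trial enrols women who could supply the reference. The plan gives them no part in the primary conclusion.

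**Working it through.** **1. Inputs.** From 6.4.2: difference 3 points, SD 2.5, power 0.90, dropout 20%, 20 per group. From 6.4.3.1: significance level 0.05. Assumed, because the documents do not say: two-sided testing, and 2.5 as the SD of a change as well as of a score.

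**2. The plan's own sample size.** Normal approximation: n = 2 × (1.960 + 1.282)² × 2.5² / 3² = 14.6, so 15 per group, and 15 / 0.8 = 18.75, so 19. By the exact t-test, 15 per group gives power 0.887 and 16 gives 0.907, so 16 are needed, and 16 / 0.8 = 20. The stated 20 per group is reproduced, for a two-sample comparison of two groups of 20. It is not a sample size for a before-after change.

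**3. What each comparison can show.**

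| Comparison | Status in the plan | What it estimates |
|---|---|---|
| Change over time in women with endometriosis | Primary outcome, no test stated | Endometriosis-specific change + discomfort common to stimulated women + drift from baseline |
| Letrozole minus placebo | The stated test and sample size | Effect of letrozole |
| Placebo-arm change minus control change | Within a secondary outcome, no test stated | Endometriosis-specific part of the change (not randomised) |

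**4. Illustration.** Suppose every stimulated woman's score rises by s points and nothing is specific to endometriosis. The documents give no value for s, so a range is shown. A paired t-test on n women has noncentrality s / (2.5 / √n). For example, with s = 1.0 and n = 16 this is 1.0 / 0.625 = 1.60, against a critical value of 2.13.

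| Assumed common rise s | Significant, 16 placebo-arm women | Significant, both arms pooled (32) |
|---|---|---|
| 0.6 | 15% | 26% |
| 1.0 | 32% | 59% |
| 1.5 | 61% | 91% |

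If the SD of change is 3.5, the pooled figures fall to 16%, 35% and 65%. A difference in change against controls stays at 5% for any rise that both groups share. The placebo-arm column is the relevant one, because pooling mixes in any letrozole effect.

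**5. Precision of the control contrast.** With 20% dropout, 16 against 16 are evaluable. The 95% half-width is 2.042 × 2.5 × √(2/16) = 1.81 points. For the placebo-arm change alone it is 2.131 × 2.5 / √16 = 1.33 points. Power for 3 points is 0.907 at SD 2.5. At an SD of change of 2.0, 3.0 or 3.5 it is 0.98, 0.78 or 0.65.

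**6. Timing.** The first primary outcome uses baseline, 6 and 12 weeks, so trigger-day discomfort cannot enter it. Study drug stops two weeks after retrieval (6.1.2), and nothing in the documents suggests that retrieval discomfort lasts to week 6. The risk lies mainly with the second outcome, read with 6.4.1 as covering trigger day and week 3.

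**The case against.** The strongest reply is that the plan does specify a two-sample test, so it is wrong to describe the primary analysis as settled on a before-after test. That stands. The documents conflict, and the percentages above belong to a paired test that the plan never names. The two-sample test still does not serve the primary objective, because both of its arms are stimulated women with endometriosis.

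A second reply is that the control comparison is already prespecified, so a common rise would be visible. This is partly right. The trial has controls, and a reader who infers that it simply repeats the earlier cohort's flaw goes too far. But the comparison is secondary and has no stated contrast.

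A third reply is that the control contrast answers a narrower question than 4.2. That also stands. It isolates the endometriosis-specific part of the change. It is not randomised, the documents describe no capsule for controls, and control eligibility is given only as age matching and no history of endometriosis. Differential regression to the mean can remain, since baseline is typically cycle day 2 (6.3.5).

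Two stronger readings are not supported:

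- Sections 3.3.1 and 6.2.2.1 list bloating as a likely effect of letrozole, which might seem to add to the case. A comparison with controls would not remove a drug effect, and the placebo arm does not take the drug.
- Section 6.3 says that "participants will be asked to complete electronic surveys about symptoms they are experiencing related to their endometriosis". A reader might infer that controls must score zero. That sentence is narrative and the survey items are not shown. Section 6.2 describes the scale more generally, as measuring the pain and symptoms that participants have. The control wording needs confirming, but a floor effect is not established.

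**Conclusion.** The point holds in a limited form. As written, no stated analysis separates an endometriosis-specific change from discomfort common to stimulated women, and the outcome sections (5.2.1, 6.4.1) do not match the test sections (6.4.2, 6.4.3.1). The risk is greatest for the second primary outcome and smaller at 6 and 12 weeks. The 15%, 32% and 61% for the placebo arm are illustrations. They rest on an assumed common rise, an SD of change of 2.5 and a paired t-test, and they show how easily a modest shared rise could be misattributed. They do not predict this trial's error rate. The control comparison is planned but has too low a status and no defined contrast. This should be changed before analysis, and the change is cheap.

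**What to change.** 1. Reconcile 5.2.1 and 6.4.1 with 6.4.2 and 6.4.3.1, so that the primary objective, its outcome, its comparison groups and its test agree.
2. Report the within-group change from baseline in the placebo arm as the description of what happens to stimulated women with endometriosis.
3. Base any endometriosis-specific conclusion on one prespecified contrast: change from baseline in placebo-arm women minus change in controls at the same survey, with its 95% CI.
4. State that this contrast is not randomised and that, with no unstimulated group, the trial does not compare stimulation with no stimulation.
5. Confirm that the VAS items given to controls ask about pelvic pain regardless of cause.

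The cost is wording, plus a check of the survey items. The controls and their surveys are already planned, and no further participants are needed under the protocol's own inputs. The downside is the wider interval (1.81 against 1.33 points) and reliance on a non-randomised comparison.

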5.2.2 Secondary and Exploratory Outcome Variables (if applicable)

- To compare the mean endometriosis pain score at baseline, 6 and 12 weeks following egg retrieval in the placebo, letrozole and control groups.
- To compare how endometriosis pain scores change throughout controlled ovarian hyperstimulation in the placebo, letrozole and control groups.
- To compare egg/embryo quantity and quality in the placebo, letrozole and control groups. This will include evaluation of: total oocyte yield per starting antral follicle count, total mature oocyte yield per oocytes collected, embryo yield per starting antral follicle count, embryo yield per oocyte retrieved, fertilization rate per mature oocyte retrieved, ovarian follicular fluid hormone levels.
- To compare pregnancy rates per embryo transfer in the placebo, letrozole and control groups.

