4.1 Hypothesis

Null hypotheses:

- a) Ovarian hyperstimulation has no impact on endometriosis-related symptoms.
- b) The use of letrozole during ovarian hyperstimulation has no impact on endometriosis-related symptoms.
- c) The use of letrozole during ovarian hyperstimulation has no impact on egg/embryo quantity or quality.
- d) The use of letrozole during ovarian hyperstimulation has no impact on pregnancy rates.

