5.3.2 Eligibility Criteria/Vulnerable Populations

Inclusion Criteria:

- Age 18-42 years
- Planning to undergo controlled ovarian hyperstimulation
- Prior diagnosis of endometriosis by one of the following: (1) surgical diagnosis (2) endometrioma on pelvic ultrasound
- Planning to freeze all retrieved oocytes/embryos prior to transfer

Exclusion Criteria:

- Hypersensitivity to Letrozole
- Any significant concurrent disease, illness, or psychiatric disorder that would compromise patient safety or compliance, interfere with consent, study participation, follow-up, or interpretation of study results

6 - Methods

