6.2 Assessments

Endometriosis associated symptoms will be evaluated using a survey modeled after the clinical survey developed by the World Endometriosis Research Foundation Endometriosis Phenome and Biobanking Harmonisation Project [10]. The survey will use a visual analog scale (VAS) to quantify pain and symptoms experienced by participants. Participants will complete this survey at their baseline ultrasound appointment for their controlled ovarian hyperstimulation cycle, the day of trigger shot, 3 weeks following egg retrieval, 6 weeks following egg retrieval and 12 weeks following egg retrieval if not pregnant. The first survey will include questions regarding any recent or prior medical or surgical treatment of their

endometriosis. It will also assess baseline use of pain medications for their endometriosis-associated pain. Study participants will be allowed to take acetaminophen when needed (Tylenol, 650 mg tablet) for pain control, but asked to record the number of tablets used.

Secondary outcomes looking at egg and embryo quality and quantity will be assessed using standard embryologists evaluation and grading of all eggs and embryos collected during controlled ovarian hyperstimulation at the University of California Center for Reproductive Health. Embryologist will be blinded to the study participants' assignments to either placebo or control group.

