6.3.1 Study Schedule

M.D. Visit	
 • M.D. to identify patient as potential study participant • M.D. discusses study with patient • M.D. to notify study team if patient interested
Meet Study Team	
 • Discuss study with patient and answer questions • Subject signs study and HIPPA consents • Randomization completed, patient provided medication
Baseline Ultrasound	
 • Completion of survey #1
Stimulation Monitoring	
 • Daily letrozole/placebo starting with first day of stimulation medications • Routine uterine and ovarian ultrasound monitoring every 1-3 days at UCSF CRH • Routine blood draws for hormonal assessment every 1-3 days at UCSF CRH (patients and providers blinded to estradiol levels)
Trigger Shot	
 • Based on routine trigger shot parameters, including mean diameter of largest follicles • Completion of survey #2 • Discontinuation of letrozole/placebo
Oocyte Retrieval	
 • Retrieve all visible follicles • Follicular fluid obtained for hormonal evaluation • Restart letrozole/placebo evening of retrieval and continue daily for 2 weeks
Embryology Lab	
 • Count total number of retrieved oocytes • Count mature oocytes and fertilization rate (if making embryos) • Assess embryo quality using UCSF CRH standard grading criteria

3 Weeks Post Retrieval	
 Completion of survey #3
6 Weeks Post Retrieval	
 Completion of survey #4
12 Weeks Post Retrieval	
 Evaluation of pregnancy status Completion of survey #5
Long-term Follow-up	
 Medical record review for pregnancy outcomes of transferred embryos and additional endometriosis treatment.

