6.4.3.2 Secondary Objectives Analyses

For our secondary outcomes, we will be evaluating the outcomes of the placebo and letrozole groups. Specifically, this will include:

- Comparison of the mean endometriosis pain score at baseline, 6 and 12 weeks following egg retrieval in the placebo, letrozole and control groups.
- Comparison of how endometriosis pain scores change throughout controlled ovarian hyperstimulation in the placebo, letrozole and control groups.
- Comparison of egg/embryo quantity and quality in the placebo, letrozole and control groups. This will include evaluation of: total oocyte yield per starting antral follicle count, total mature oocyte yield per oocytes collected, embryo yield per starting antral follicle count, embryo yield per oocyte retrieved, fertilization rate per mature oocyte retrieved, follicular fluid hormone levels.
- Comparison of pregnancy rates per embryo transfer in the placebo, letrozole and control groups.

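### Pregnancy is compared only per embryo transfer, an event after randomisation; a rate per randomised woman should be reported beside it

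*Combined protocol and SAP*

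**What the plan says.** Hypothesis (d) in section 4.1 is that "The use of letrozole during ovarian hyperstimulation has no impact on pregnancy rates". Section 5.2.2 turns this into an outcome, "To compare pregnancy rates per embryo transfer in the placebo, letrozole and control groups", and section 6.4.3.2 repeats it as the analysis: "Comparison of pregnancy rates per embryo transfer in the placebo, letrozole and control groups". These are the only two places that give pregnancy a denominator. The synopsis lists pregnancy rates in the three groups without one.

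Randomisation takes place at enrolment (6.3.1, 6.3.4), before stimulation, retrieval and any transfer. Hypothesis (c) is that "The use of letrozole during ovarian hyperstimulation has no impact on egg/embryo quantity or quality".

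Not every participant need have a transfer. The freeze-all inclusion criterion in 5.3.2 reads "Planning to freeze all retrieved oocytes/embryos prior to transfer", so women freezing oocytes qualify, and the laboratory row of 6.3.1 reads "Count mature oocytes and fertilization rate (if making embryos").

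On data, 6.3.1 schedules an evaluation of pregnancy status at 12 weeks after retrieval, with no restriction to women who had a transfer. Section 6.2 asks for the last survey at "12 weeks following egg retrieval if not pregnant", which also requires status to be known then. Long-term follow-up is "Medical record review for pregnancy outcomes of transferred embryos and additional endometriosis treatment"; 6.3.5 describes periodic chart review and sets no end date. Section 6.4.1 states intention to treat in general terms.

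**The concern.** Hypothesis (d) is about using letrozole during stimulation, so the comparison that randomisation protects is between all 20 women assigned to letrozole and all 20 assigned to placebo. A per-transfer rate conditions on something that happens later and that treatment might influence. A woman with no usable embryo, or with oocytes in storage, contributes nothing. A woman with two transfers contributes twice, and the two results are not independent.

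The intention-to-treat sentence does not settle this. It keeps each woman in her assigned arm, but it does not put a woman without a transfer into a denominator made of transfers. The yield measures in 5.2.2 do not settle it either. Their denominators are antral follicles or oocytes, and none gives the number of women reaching transfer by arm.

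At stake is how one of the four stated null hypotheses is read. If letrozole altered the share of women who get to transfer, the planned analysis could show no difference while pregnancy among the randomised women differed, in either direction.

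**Working it through.** **The plan's own figure.** The only sample size given is for pain (6.4.2): a 3-point difference, SD 2.5, 90% power, 20% dropout. Taking the 0.05 level of 6.4.3.1 as two-sided, a two-sample t-test needs 15.6, so 16 per arm; 16 / (1 − 0.20) = 20 per arm, 40 in total. That reproduces. The documents give no power, expected pregnancy rate or share reaching transfer for the pregnancy outcome.

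**Inputs.** 20 women per randomised arm (5.3.1). Assumed, because the documents give no figures: one transfer per woman, the same success rate per transfer in both arms, and a share reaching transfer that may differ by arm.

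**Formula.** Rate per woman = share reaching transfer × rate per transfer. With equal per-transfer rates, the per-transfer difference is 0 and the per-woman difference is the gap in share × the rate per transfer.

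**Worked case.** Shares 80% v 60%, success 50%:
- transfers: 0.80 × 20 = 16 and 0.60 × 20 = 12
- per transfer: 8/16 v 6/12 = 50% v 50%, difference 0 (Newcombe 95% CI −33 to +33 points)
- per woman: 8/20 v 6/20 = 40% v 30%, difference 10 points (Newcombe 95% CI −18 to +36 points; Fisher p = 0.74)

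**Range.** Absolute per-woman difference when the per-transfer difference is exactly 0:

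| Shares reaching transfer | Success 40% | Success 50% | Success 60% |
|---|---|---|---|
| 80% v 80% | 0 | 0 | 0 |
| 80% v 60% | 8 points | 10 points | 12 points |
| 70% v 40% | 12 points | 15 points | 18 points |

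Swapping the arms reverses the sign. The first row is the case in which letrozole leaves the share unchanged.

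**Precision of a per-woman comparison.** Fisher exact power, two-sided 0.05, 20 per arm: 6% for 40% v 30%, 16% for 50% v 30%, 19% for 40% v 20%. If status is unknown for 20% of women (16 known per arm), power for 40% v 20% is 13%.

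**Dilution by oocyte freezing.** Suppose a quarter of each arm has no transfer because oocytes were frozen. Then 40% v 20% becomes 0.75 × 40 = 30% v 0.75 × 20 = 15% (power 12%). At one half it becomes 20% v 10% (power 7%).

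**The case against.** The strongest reply is that the harm is conditional and the plan's evidence points away from it. Section 2.1.2 cites no effect of letrozole on oocyte or embryo yield, and 6.1.3 expects no negative effect on cycle outcomes from withholding estradiol results. Listing hypothesis (c) as a null to be tested is not evidence of an effect. A large effect on yield would probably also show in the yield comparisons of 5.2.2. All of this stands, and the transfer gap used above is an assumption.

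A second reply is that a per-woman rate may tell the reader less. In a freeze-all population many transfers could fall after any early cut-off, and 7.15 plans completion within 6 months of full accrual. The rate would then partly reflect transfer scheduling and the intention to store oocytes. This also stands. It is why the per-woman rate should be added and the per-transfer rate kept; the two answer different questions.

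A reader might go further and infer that the protocol leaves no way to compare pregnancy among the women as randomised. The documents do not support that. The synopsis and hypothesis (d) leave the denominator open, and the 12-week status check covers women whether or not they had a transfer. What is missing is a defined analysis of data that are already planned.

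**Conclusion.** The point holds as a gap in the defined analysis. Where the plan specifies the pregnancy comparison, it does so only per transfer, and women with no transfer drop out of it. Under the assumed shares and success rates, a per-transfer difference of zero can coexist with a per-woman difference of about 8 to 18 points in either direction. If letrozole does not change who reaches transfer, the difference is zero.

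A reader might infer that letrozole will distort the pregnancy result. Nothing in the documents shows that it changes the share reaching transfer, and the evidence cited in 2.1.2 suggests that it does not affect yield. The outcome is secondary and unpowered on either denominator, so the consequence is for the interpretation of hypothesis (d). The sample size and the primary pain analysis are not affected.

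**What to change.** In 5.2.2 and 6.4.3.2, for letrozole v placebo:

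- Report also the proportion of randomised women pregnant by one pre-stated time, the same for every woman, with the risk difference and 95% CI. Use the 12-week status check in 6.3.1 and the chart review in 6.3.5.
- Count women known not to be pregnant, including those with no transfer, as not pregnant. Handle unknown status under 6.4.5.
- Report by arm the number of women reaching transfer and the reasons for none.
- Keep the per-transfer rate alongside, limited to first transfers or with clustering by woman.

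The cost is wording in two sections and a stated cut-off; if the cut-off is later than 12 weeks, it must agree with the completion plan in 7.15. No new visit or larger sample is needed. The downside is that an early cut-off misses later transfers and women freezing oocytes dilute the comparison. The per-woman result should therefore be read as an imprecise estimate with its interval, and not as proof of no effect.
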